Experimental Design: Two TC teams (APN, RD and Psy. Fellow) will be constituted and trained, one each at NCH and AIDHC. A backup for each team member will also be identified and trained. Families will be randomized by [name] staff to TC-IP (n=50), TC-TH (n=50) or UC (n=50), using a prepared randomization list, stratified by insulin modality (pump or injections) and HbA_{1c} (\leq or $>$ 8.7%). We rejected randomization by sites due to logistical obstacles and since site differences might obscure detection of treatment effects. Randomization at the level of families reduces those concerns but introduces contamination issues as TC elements could intrude into UC visits. Efforts to counter this potential confound are described below. Each youth/parent will receive the assigned care (TC or UC) for approximately 4 successive follow-up visits across approximately 12 months. This period is adequate to detect clinically meaningful changes in HbA_{1c} and adherence. The design also permits exploratory analyses of modality of care (Face-to-Face vs. Telehealth), gender, race and ethnicity as moderators of treatment outcomes.

Treatment Conditions: The original RCT design is shown above. Treatment conditions include Usual Care and Transdisciplinary Care delivered in person or through telehealth. Elements of TC care are employed with some adolescents with T1D at AIDHC (i.e., APN and Psychologist see some patients together); this is much less true at NCH. AIDHC patients who have had such a visit within 12 months are ineligible for this study.

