Analytic Plans Primary endpoints are change in HbA_{1c} and DSMP-SR total score (treatment adherence) over 1 year. Secondary endpoints are: # of severe hypoglycemic events (Hypoglycemia Diary); measures of glycemic variability at each visit; and questionnaires obtained quarterly. The Full Analysis Set will include those who provide data at ≥ 1 follow-up visit. The Completer Analysis set will include those who provide data at all follow-ups. Efficacy analyses will be done on both sets.³¹³⁻³¹⁵ We will use multiple imputation for treatment of missing data.³¹³⁻³¹⁵ Obtained data will be summarized in graphs and tables. Categorical variables will be summarized by frequencies and percentages; continuous variables by mean, median, standard deviation (or SEM), minimum and maximum. Data will be summarized by primary group (UC and TC), secondary group (TC-TH, TC-IP, TC-IP/TH, TC-TH/CH) and measurement points.^{316,317} Model assumptions will be checked before analyses, and appropriate transformations or non-parametric methods will be used when indicated. For summarization of normally distributed data, group means and SEM will be presented. In case of substantial deviation from normality, boxplots will be presented. Exploratory subgroup analyses (e.g. race, ethnicity, gender, SES, secondary group) will be conducted as needed.^{318,319} Most tests will be performed against a two-sided alternative at the $\alpha = 0.05$ significance level and a 95% confidence interval and/or a p-value will be provided for inferential purposes. Data from both clinics will be pooled for analyses.^{316,317} All analyses will be done using the most recent version of SAS, SPSS, R or M-Plus.³¹⁵⁻³²² Demographic variables (age, gender, race, ethnicity, family structure, marital status, SES) and baseline values of primary and secondary end points, and questionnaire results will be summarized by group. If the normality assumption holds, t-tests of continuous baseline variables and Fisher exact test/chi-square test/CMH test for categorical variables will be used to compare the TC and UC groups at baseline; one-way ANOVA will be used for comparisons of secondary groups. The statistician will select analytic methods based on data distributions and any imbalanced baseline scores.³²³ Linear mixed effects modeling (continuous outcomes) or generalized linear mixed modeling (categorical outcomes) is planned for the hypotheses below.³¹⁵⁻³²² Treatment group (UC vs TC) and demographic characteristics will be fixed effects in these models, while site, physician, and within-subject effects will be random effects. The same analyses will be attempted for secondary groups, sample size permitting. We will use Holmbeck's methods³²⁴ to evaluate baseline demographic variables and questionnaire scores as moderators of TC-UC effects on primary outcomes and to evaluate mediation of effects on primary endpoints. Candidate mediators are variables that are obtained serially concurrent with the primary endpoints at ≥ 3 visits.

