
Sample Size and Statistical Power: Recruitment ended at the end of March 2020. A total of 115 families were recruited. Allowing for some attrition prior to randomization, a sample of 100 patients (65 TC and 35 UC) yields 87.4% power to detect a clinically meaningful group differences in mean HbA_{1c} of 0.5% (~0.7 SD) versus the alternative of equal means using a t test with $p = .05$. Limiting recruitment to those with HbA_{1c} = 7.5-10.0% is anticipated to reduce the SD from 1.5% for the general adolescent T1D population to 0.7%, boosting effective statistical power for the RCT. The predicted 12-month means are 8.1% (TC) and 8.6% (UC). If the SD is 1.0%, our power is reduced to 71.3%; if it is 1.5% as in the general population, our power is 50.9%. This sample size also achieves power of 78.2% to detect a clinically meaningful mean differences in the DSMP-SR

total score of 7.0 points (~0.6 SD) at 1 year. The estimated mean values are 63.0 (TC) and 56.0 (UC). This preliminary trial will yield rich data that could be used to guide the sampling plan for a future, more ambitious, multi-center trial.³²⁵⁻³²⁷ The following hypotheses will be tested:

Hypothesis 1: Compared with UC patients, those randomized to TC will have significantly more favorable primary (HbA_{1c} and DSMP-SR scores) and secondary (frequency of severe hypoglycemia and level of glycemic variability) diabetes management outcomes at their 6, 9, and 12 month follow-up visits.

Hypothesis 2: Compared with UC patients, those randomized to TC will demonstrate more favorable scores on the T1DAL, PAID, and CPI at follow-up measurements.

Hypothesis 3: Significantly higher scores will be obtained on the DCI completed by HCPs describing TC care compared to HCPs describing UC care.

Hypothesis 4: Effects of TC on HbA_{1c} and DSMP-SR scores will be moderated by demographic variables (youth age, family SES, # of adult caregivers in the home) and by baseline scores on the T1DAL, PAID, and CPI. More benefit from TC will accrue to youth who are younger, from two-parent families with higher SES, and with more favorable scores on the T1DAL, PAID and CPI.

Hypothesis 5: Effects of TC on HbA_{1c} and DSMP-SR scores will be mediated by changes in scores on the T1DAL, PAID, and CPI. More benefit from TC will accrue to youth with favorable changes in T1DAL, PAID and CPI scores during the 12 months of the study.

[figure not shown]

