parent or legally appointed caregiver of an enrolled patient; Primary or shared responsibility for monitoring the medical care of the youth with T1D; Able to complete study questionnaires in English; Stated intent to continue medical care for T1D at Nemours Children's Clinic for 12 months following enrollment. Two parents of the same child may participate, in which case one set of the parent-administered questionnaires will be completed at each assessment point by both parents together. Randomization will be at the level of families; for any family with two or more eligible adolescents, all of those adolescents would be randomized to the same condition. The HCPs who will implement the clinical aspects of this protocol will also be viewed as research participants and will sign IRB-approved Informed Consent Forms prior to their involvement in the research. These persons will complete questionnaires and post-study qualitative interviews about their satisfaction with the respective care models and they will also be the subject of certain questionnaires completed by parents and adolescents. Also, HCPs who see study patients will complete certain questionnaires and a qualitative interview about their perceptions of the TC model at the end of the study. Data for cost-effectiveness analyses will be collected throughout the study from parents and from participants' electronic medical records and analyzed after the RCT is complete.

Sources of research data

Qualitative research component: Transcripts of crowdsourced responses to questions posed to the Adolescent, Parent and HCP Crowds will be downloaded directly from Yammer.com and then edited to remove any identifying information. Each response will be coded for qualitative themes as described above. Qualitative interviews of representatives of key stakeholder groups will be audio-recorded and then transcribed verbatim without any personal identifiers used. Once transcribed, the audio recordings will be erased, eliminating any link between the interview respondents and their comments.

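### Families are randomised and siblings share an arm, but the planned model has no family term; if any siblings enrolled, the TC-UC standard errors would be slightly too small

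*Combined protocol and SAP*

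**What the plan says.** Two places in the combined protocol and SAP name the family as the randomised unit. Section 3.4, Experimental Design, weighs family-level against site-level allocation: "Randomization at the level of families reduces those concerns but introduces contamination issues". Section 6, Quantitative (RCT) Research Component, adds the sibling rule: "for any family with two or more eligible adolescents, all of those adolescents would be randomized to the same condition". No eligibility criterion in section 3.4 or section 6 limits a family to one adolescent.

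The randomisation list is stratified by insulin modality and by HbA1c, cut at 8.7% (section 3.4, Experimental Design). Both belong to the adolescent and can differ between siblings. The documents do not say which sibling sets the family's stratum.

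On the model, section 3.4, Analytic Plans, states: "Treatment group (UC vs TC) and demographic characteristics will be fixed effects in these models", "while site, physician, and within-subject effects will be random effects". No family effect, family-clustered variance or one-adolescent-per-family rule appears in the documents.

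Sample Size and Statistical Power counts recruitment in families ("A total of 115 families were recruited") and power in patients ("a sample of 100 patients (65 TC and 35 UC) yields 87.4% power"), using an ordinary t test.

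**The concern.** When siblings are allocated together, the analysis should allow for their correlation. Siblings share a household and an arm, so their HbA1c, adherence and questionnaire scores may be more alike than those of unrelated adolescents. The planned terms do not represent this. Site and physician effects capture only what all patients of that site or physician share, and the within-subject effect links the repeated measurements of one adolescent. Correlation left over between siblings in the same arm makes the estimated variance of the TC-UC difference too small, so confidence intervals are too narrow and the type I error exceeds its nominal level. The stratification gap is secondary: a family whose adolescents differ in insulin modality or fall on either side of 8.7% belongs to two strata but receives one allocation.

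**Working it through.** **The plan's own figure.** Inputs from Sample Size and Statistical Power: 65 TC and 35 UC, HbA1c difference 0.5%, SD 0.7%, t test at 0.05; taken as two-sided, as Analytic Plans says of most tests. The standard error is 0.7 × √(1/65 + 1/35) = 0.147, the noncentrality is 0.5/0.147 = 3.41 on 98 df, and power is 92.1%. The stated 87.4% is not reproduced. For DSMP-SR (0.6 SD) the same method gives 80.9% against a stated 78.2%. Clustering does not explain these gaps: the powers stated for SD 1.0% and 1.5% (71.3% and 50.9%) lie above the two-sided values (65.6% and 35.0%), not below. That is a separate matter, and the present point does not depend on it. The recomputed values serve as the baseline below.

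**Assumptions not in the documents.** The number of sibling pairs k (2, 5 or 10 among N = 100) and the residual family correlation ρ (0.2, 0.4 or 0.6), meaning what remains after the site, physician and demographic terms. Pairs are taken to be spread over the arms in proportion to arm size.

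**Design effect.** DE = 1 + (Σm²/Σm − 1)ρ, where m is the number of adolescents per family. With k pairs and the rest singletons, Σm = 100 and Σm² = (100 − 2k) + 4k = 100 + 2k, so DE = 1 + (2k/100)ρ.

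**Type I error when family is ignored.** 2 × [1 − Φ(1.96/√DE)]. For k = 5 and ρ = 0.4: DE = 1 + 0.10 × 0.4 = 1.04, √DE = 1.0198, 1.96/1.0198 = 1.922, giving 5.5%.

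| Pairs | ρ | DE | Effective N (100/DE) | Type I error |
|---|---|---|---|---|
| 0 | any | 1.000 | 100 | 5.0% |
| 2 | 0.2 | 1.008 | 99.2 | 5.1% |
| 2 | 0.6 | 1.024 | 97.7 | 5.3% |
| 5 | 0.4 | 1.040 | 96.2 | 5.5% |
| 10 | 0.2 | 1.040 | 96.2 | 5.5% |
| 10 | 0.4 | 1.080 | 92.6 | 5.9% |
| 10 | 0.6 | 1.120 | 89.3 | 6.4% |

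**Power once family is accounted for** (variance of the difference multiplied by DE). HbA1c at SD 0.7% goes from 92.1% to between 91.9% and 89.0%. DSMP-SR goes from 80.9% to between 80.6% and 76.4%. In the middle case (5 pairs, ρ = 0.4) they are 91.1% and 79.4%.

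**The case against.** The strongest reply is that the sibling rule is a contingency and nothing shows it was ever used. Section 8 plans 150 adolescents and 150 parents, the Specific Aims speak of 150 families, and the power section moves from 115 families to 100 patients without distinguishing the two. That reads like about one adolescent per family. Each sibling would also have to meet the age, diabetes-duration and HbA1c criteria. With no sibling sets, the stated model needs no family term. This stands, and it makes the point conditional.

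A second reply is that part of any sibling similarity is already absorbed. Site and physician are random effects, and demographic characteristics are fixed effects; several of those listed (race, ethnicity, family structure, marital status, SES) are largely family-level. This also stands. It is why ρ is treated as a residual correlation and given as a range, but it does not show that the residual is zero.

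Third, any rule fixed in advance for placing a multi-adolescent family still gives a valid random allocation, and such a rule could sit in the procedure manual or the randomisation list, which are not available here. That stands too, so the stratum question is one of record-keeping.

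A reader might infer more: that siblings were in fact enrolled and analysed as independent, that they attended visits together, or that one parent rated both and so DSMP-SR is worst affected. The documents support none of these. They report no sibling set and do not mention joint sibling visits. The provision on joint completion of questionnaires concerns two parents of the same child. DSMP-SR has adolescent and parent reports, and the plan does not say which gives the primary score.

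**Conclusion.** The mismatch is in the text: the family is randomised, and the stated model does not account for it. The latitude given to the statistician in Analytic Plans concerns data distributions and baseline imbalance, and does not reach family clustering. The consequence is conditional and small. Under the assumed 2 to 10 pairs and residual correlation of 0.2 to 0.6, the type I error would be about 5.1% to 6.4%, and accounting for family would cost about 0.2 to 3.1 points of HbA1c power. Both inputs are assumptions; the upper end has one adolescent in five belonging to a sibling pair, for which the documents give no support. With no siblings the effect is exactly zero. The finding does not show that the trial's standard errors are wrong, and it is a low-priority improvement.

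**What to change.** In the HbA1c, DSMP-SR and questionnaire models, account for family as the randomised unit with a family random intercept, subject nested in family. With nearly all families contributing one adolescent, that variance may be hard to separate from the subject effect. The plan should therefore name family-clustered standard errors as the fallback if the intercept cannot be estimated.

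Keep all randomised adolescents who qualify for the Full Analysis Set, and use one adolescent per family only as a sensitivity analysis. Making that restriction primary would drop randomised participants against the plan's own analysis-set definition; with 10 pairs it would discard 10 of 100.

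Report the numbers of families and adolescents randomised. Because recruitment ended in March 2020, record how any multi-adolescent family was actually placed in a stratum instead of setting a rule afterwards. If there were none, one sentence closes the point.

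The cost is one model term and a few sentences, with no new data. Intervals would be slightly wider if siblings were enrolled; otherwise there is no downside.

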7. REPRESENTATION OF WOMEN AND MINORITIES

We expect to enroll about 50% female adolescents with T1D, and we expect that about 80-90% of participating parents will be women. Among HCPs and representatives of third party payers, we expect at least 50% representation of females, but this will be dependent upon the specific employees who are eligible for

participation. We plan oversampling of racial/ethnic minorities so that both the Qualitative and Quantitative components of the research enroll a sample reflecting at least 25% representation of racial and ethnic minorities. The race/ethnicity distribution of HCP Crowd members may be slightly less diverse than that for the Adolescent and Parent Crowds. Separate Targeted/Planned Enrollment Tables for the Crowdsourcing/Qualitative Research and RCT aspects of the proposed work accompany this application.

8. TARGETED/PLANNED ENROLLMENT TABLE

Study Title: Trans-Disciplinary versus Usual Care for Type 1 Diabetes in Adolescence

QUALITATIVE RESEARCH COMPONENT: 120 adolescents with type 1 diabetes; 120 parents of youth with type 1 diabetes; 30 HCPs; 10 representatives of third party payers.

TARGETED/PLANNED ENROLLMENT: Number of Participants			
Ethnic Category	Sex/Gender		
	Females	Males	Total
Hispanic or Latino	15	15	30
Not Hispanic or Latino	105	105	210
Ethnic Category: Total of All Participants *	120	120	240
Racial Categories			
American Indian/Alaska Native	0	0	0
Asian	3	3	6
Native Hawaiian or Other Pacific Islander	0	0	0
Black or African American	12	12	24
White	105	105	210
Racial Categories: Total of All Participants *	120	120	240

Targeted/Planned Enrollment Table

Study Title: Trans-Disciplinary versus Usual Care for Type 1 Diabetes in Adolescence

RANDOMIZED, CONTROLLED TRIAL: 150 adolescents with type 1 diabetes; 150 parents.

TARGETED/PLANNED ENROLLMENT: Number of Participants (Adolescents)			
Ethnic Category	Sex/Gender		
	Females	Males	Total
Hispanic or Latino	11	10	21
Not Hispanic or Latino	64	65	129
Ethnic Category: Total of All Participants *	75	75	150
Racial Categories			
American Indian/Alaska Native	0	0	0
Asian	0	0	0
Native Hawaiian or Other Pacific Islander	0	0	0
Black or African American	10	11	21
White	65	64	129
Racial Categories: Total of All Subjects *	75	75	150
TARGETED/PLANNED ENROLLMENT: Number of Participants (Parents)			
Ethnic Category	Sex/Gender		
	Females	Males	Total
Hispanic or Latino	15	6	21
Not Hispanic or Latino	110	19	129
Ethnic Category: Total of All Participants *	125	25	150
Racial Categories			
American Indian/Alaska Native	0	0	0
Asian	0	0	0
Native Hawaiian or Other Pacific Islander	0	0	0
Black or African American	15	5	21
White	110	19	129
Racial Categories: Total of All Subjects *	125	25	150

9. REPRESENTATION OF CHILDREN

All patients with T1D will be below the age of 17 at enrollment. The 11-<17 year old age range was chosen since this is the age range during which T1D adherence issues emerge and in which effective management of the condition becomes increasingly challenging. Major epidemiologic studies indicate that this age group achieves targeted levels of HbA1c infrequently (< 25% of patients) compared with other age groups.

10. VERTEBRATE ANIMALS (Not Applicable)

11. SELECT AGENT RESEARCH (Not Applicable)

12. MULTIPLE PI LEADERSHIP PLAN (Not applicable)

13. CONSORTIUM/CONTRACTUAL ARRANGEMENTS

[name]., Chatlos Professor of Nursing at the University of Central Florida College of Nursing, will provide expert consultation in qualitative research methods and community-based participatory research for this work. The details of her involvement are summarized in the research strategy and her time and effort is reflected in the budget and budget justification.

14. LETTERS OF SUPPORT

[name] letter of support accompanies this application.

15. RESOURCE SHARING PLAN

Upon acceptance for publication of journal articles addressing the primary specific aims and hypotheses as delineated in this application, the final data set will be stripped of all HIPAA-defined personal identifiers and then archived in a data repository that is accessible to interested members of the public. Even though the final dataset will be stripped of identifiers prior to release for sharing, there may remain the possibility of deductive disclosure of subjects with unusual demographic characteristics. Thus, we will make the data and associated documentation available to users only under a data-sharing agreement that provides for: (1) a commitment to using the data only for research purposes and not to attempt to identify any individual participant; (2) a commitment to securing the data using appropriate computer technology; and (3) a commitment to destroying or returning the data after analyses are completed.

Other "deliverable" resources that can be made available to interested parties after the proposed work is complete will include the curriculum for training health care providers in the Trans-Disciplinary Care model, and the procedure manual for this study that will detail the structure, process and evaluation of the care model. These resources could be exceptionally valuable should the proposed work progress on to the design and implementation of a more ambitious and definitive multi-center trial of the TC model.

APPENDIX

- Tentative qualitative interview questions for parents, adolescents and health care providers about the structure and process of a tentative trans-disciplinary care model
- Tentative qualitative interview questions for members of the trans-disciplinary care team regarding the adequacy of the TC training curriculum
- Revised post-RCT qualitative interview questions for parents and adolescents about the advantages and disadvantages of trans-disciplinary care
- Tentative post-RCT qualitative interview questions for representatives of third party payers about the economic viability of trans-disciplinary care, given the results of the RCT
- Copy of parent-completed health care utilization record used in the JDRF continuous glucose monitoring trial.
- Copies of questionnaires to be administered during the RCT.
- NIDDK approved DSMP/DSMB description for randomized controlled trial
